8.5.3. Management of QTcF Prolongation

If > 60 ms change from baseline occurs OR QTcF > 500 ms, TRC253 should be held and electrolytes evaluated and repleted (if required). Other possible etiologies should be investigated (e.g., cardiac ischemia), and telemetry monitoring initiated if indicated. Patients who experience QTcF prolongation > 500 ms or > 60 ms change from baseline without electrolyte abnormalities should permanently discontinue treatment except in patients who are responding to the drug, in whom a favorable benefit-risk exists per the Investigator and where the patient re-consents to continued treatment. Patients discontinued due to a > 60 ms change from baseline OR QTcF > 500 ms should also be monitored by a cardiologist, with a minimum of weekly QTcF assessments for at least two weeks and one QTcF assessment after four weeks.

If > 60 ms change from baseline occurs OR QTcF > 500 ms patients can be re-challenged at the same dose if there were electrolyte abnormalities present during the initial finding of QTcF prolongation, and after repleting electrolytes, the QTcF recovers to < 450 ms, and a favorable benefit-risk exists per the Investigator. Re-challenge patients should re-consent to continued treatment.

If there were no electrolyte abnormalities present initially during the finding of QTcF prolongation, but the patient is responding and a favorable benefit-risk exists per the Investigator patients should dose reduce to 240 mg and may resume treatment at this lower dose after recovery of the QTcF to < 450 ms. An additional dose reduction to 200 mg should be implemented for a subsequent >60 ms change from baseline or QTcF > 500 ms seen at the 240 mg dose level.

While ECG readings at the sites will be used for patient management purposes, an additional central read will be performed. Sites will receive clinical alerts for QTcF values > 500 ms and for > 60 ms changes from baseline as determined by the third-party vendor.

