	Grade 3 thrombocytopenia with hemorrhage or Grade 4 thrombocytopenia
Non-hematologic	Grade \geq 3 non-hematological toxicity, with the following exceptions: 
 • Grade 3 nausea, vomiting, or diarrhea lasting < 72 hours in the absence of maximal medical therapy • Grade 3 fatigue < 5 days
	Grade \geq 3 QTcF prolongation or increase in QTcF of > 60 ms from baseline

	Missing > 7 days doses for toxicity in Cycle 2
	Grade \geq 1 seizure

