8.5.2. TRC253 Dose Modification/Dose Interruptions

The phase 2 dose of TRC253 is 280 mg daily.

Dose modifications and/or dose interruptions may be warranted for patients who experience toxicities. Patients with toxicities that are manageable with supportive care (i.e., nausea or vomiting) may not warrant dose reduction. For any occurrence of grade 2 or greater non-hematologic toxicity, study drug may be held until toxicities have resolved or improved to grade 1 or baseline, then resume drug at the same dose if the event was a tolerable grade 2 (at PI's discretion). Dose interruption or reduction to 240 mg is also permitted for grade 2 toxicity at the discretion of the investigator. If the event is grade 3 or 4, the study drug dose should be reduced to 240 mg when resuming drug administration. For a subsequent episode of a grade 3 adverse event, dose reduction to 200 mg is warranted once patient has recovered. If there is no recovery to \leq grade 1 or baseline after a 21 day delay, the patient should be discontinued from the study.

Dose modifications or interruptions may be necessary for liver enzyme elevations. For grade 2 aspartate aminotransferase (AST) or alanine aminotransferase (ALT) elevation (>3 times to <5 times the upper limit of normal), without signs of severe liver damage, stop study drug until liver enzymes return to baseline values. Once liver enzymes have returned to baseline values, treatment may be reintroduced at 240 mg. Discontinue study drug for AST or ALT elevations $>5X$ ULN or for patients who meet Hy's Law criteria (concurrent elevation of AST or ALT $>3X$ ULN and total bilirubin $>2X$ ULN).

Dosage modification or treatment interruptions may also be necessary for patients with diarrhea or nausea/vomiting. Treat diarrhea at first signs with adequate hydration and antidiarrheal medication (e.g., loperamide), and consider treatment interruption if diarrhea continues. For grade ≥ 3 adverse events, first episode, patient should hold TRC253 until \leq grade 1 or baseline, then may restart at 240 mg. After a second episode of a grade 3 adverse event, further dose reduction to 200 mg is warranted once patient has recovered. If no recovery to \leq grade 1 or baseline after a 21 day delay, the patient should be discontinued from the study.

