Nausea or vomiting should be treated with supportive care including anti-emetic therapy and, if persistent, may require treatment interruption or dose reduction. For grade ≥ 3 adverse events, first episode- patient should hold TRC253 until \leq grade 1 or baseline, then may restart at 240 mg. After a second episode of a grade 3 adverse event, dose further dose reduction to 200 mg is warranted once patient has recovered. If no recovery to \leq grade 1 or baseline after a 21 day delay, patient should be discontinued from the study.

Further dose reductions below 200 mg may be permitted following discussion with the Sponsor.

Additionally, in Part 2, patients should be considered for dose reduction if they experience toxicities outlined in [Table 6](#).

Dose interruptions are allowed for a maximum of 21 days; if dosing is not restarted in that time frame, the patient should be discontinued from the study.

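### After a grade 3 or 4 QTcF event with an electrolyte abnormality, Sections 8.5.2 and 8.5.3 give different resumption doses, and neither says which governs

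*Combined protocol and SAP*

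**What the plan says.** Section 8.5.2 opens with the Part 2 dose: "The phase 2 dose of TRC253 is 280 mg daily". Its general rule has a wide scope: "For any occurrence of grade 2 or greater non-hematologic toxicity, study drug may be held" until recovery. A tolerable grade 2 event may resume unchanged. For worse events the text is: "If the event is grade 3 or 4, the study drug dose should be reduced to 240 mg when resuming drug administration". A later grade 3 episode leads to 200 mg, and failure to recover within 21 days means discontinuation. QTcF is not excepted. Further on, the same section says that in Part 2 "patients should be considered for dose reduction if they experience toxicities outlined in" Table 6. The non-hematologic block of Table 6 (Section 5.2) includes grade 3 or higher "QTcF prolongation or increase in QTcF of > 60 ms from baseline".

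Section 8.5.3 deals with QTcF prolongation alone. Its triggers are a rise of more than 60 ms from baseline or a value above 500 ms. It then makes a distinction that Section 8.5.2 does not:

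- With an electrolyte abnormality, "patients can be re-challenged at the same dose if there were electrolyte abnormalities present during the initial finding of QTcF prolongation", once electrolytes are repleted, "the QTcF recovers to < 450 ms, and a favorable benefit-risk exists per the Investigator", and the patient re-consents.
- Without one, a responding patient with favorable benefit-risk resumes at 240 mg after recovery, with a step to 200 mg if the event recurs on 240 mg. Other patients stop permanently.

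The ECG rows of Tables 7 and 8 refer sites to Section 8.5.3 for QTcF prolongation, and so does withdrawal criterion 8 in Section 7.4.3.

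**The concern.** Both sections can apply to the same event. A site that starts from the general grade 3 or 4 sentence resumes at 240 mg. A site that starts from the QTcF section may resume at the dose the patient was taking. Neither section mentions the other on this question.

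The event is not peripheral. Sections 2.4 and 2.4.1 report QTcF prolongation as the most common related reaction, the single DLT, and the reason for two discontinuations. An instruction on how to restart after it should have one reading. There is also a smaller statistical interest: ECG intervals are summarised by dose group and cohort (Section 14.4.3), and Week 12 PSA response is reported for cohorts nominally at 280 mg.

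**Working it through.** **Side by side.** Take a Part 2 patient on 280 mg with a recovered QTcF event above an 8.5.3 trigger, assumed to be grade 3 or 4.

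| Situation | Section 8.5.2, general rule | Section 8.5.3 |
|---|---|---|
| First event, electrolytes abnormal | 240 mg | 280 mg permitted, with conditions |
| First event, electrolytes normal, patient responding | 240 mg | 240 mg |
| Second grade 3 event after restarting at 280 mg | 200 mg | no explicit step |
| Longest hold | 21 days | not stated |

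Only the first row is a direct disagreement. The second row agrees. The last two show that Section 8.5.3 is not self-contained: its 200 mg step covers only recurrence on 240 mg, and the hold limit stands in Section 8.5.2 and withdrawal criterion 5. A site must therefore read the two sections together.

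The Table 6 sentence adds a third strength of instruction. The same event meets a direction to reduce, a direction to consider reducing, and permission not to reduce.

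**Size of the dose difference.** (280 − 240)/280 = 40/280 = 14.3%.

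**How many patients.** The counts in Section 2.4.1 are 22 of 34 with any QTcF prolongation and 2 of 34 at grade 3. Check: 22/34 = 64.7% (printed 65%); 2/34 = 5.9% (printed 6%). Applied to about 60 Part 2 patients, 2/34 × 60 = 3.5. The share with an electrolyte abnormality is not given; letting it run from 0 to 1 gives 0 to about 4 patients.

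This is an order of magnitude only:

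- The exact 95% interval for 2/34 is 0.7% to 19.7%, or 0.4 to 11.8 events in 60.
- The 34 patients pool starting doses from 40 to 320 mg and both study parts. The DLT occurred at 320 mg.
- Section 2.5.1 describes a group with no grade 3 or higher QTcF event. Its printed 40% and 7% fit a denominator of 15 (6/15 and 1/15), but the opening of that text is not available, so its dose cannot be confirmed.
- Exclusion criterion 14 removes chronic hypokalemia and hypomagnesemia, which should narrow the electrolyte subset.

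**The case against.** The strongest reply is that the specific rule governs the general one. Section 8.5.3 is the QTcF section, and both schedules and withdrawal criterion 8 send QTcF events there. The protocol uses this pattern elsewhere: the liver paragraph in Section 8.5.2 is stricter for grade 2 transaminase elevations than the general grade 2 rule. And if the general grade 3 or 4 sentence also bound QTcF events, the electrolyte distinction in Section 8.5.3 would make no difference to the resumption dose for those grades. This is a good argument, and probably how many sites would read the text. It remains an inference, because no sentence states it, and Section 8.5.2 itself brings QTcF in through Table 6.

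A reader might infer more than the documents support:

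- *That Section 8.5.2 makes 240 mg compulsory.* Its wording is advisory, and its Table 6 sentence asks only that reduction be considered. Section 8.5.3 is permissive and rests on the Investigator's judgement, so some variation in dose is built in.
- *That every restarted patient is affected.* Those without an electrolyte abnormality who may continue resume at 240 mg under both sections.
- *That every event meeting an 8.5.3 trigger is grade 3 or 4.* The triggers are in milliseconds and the CTCAE grades are not reproduced. Table 6 lists the grade and the 60 ms rise as alternatives. For a tolerable grade 2 event, Section 8.5.2 also allows the same dose, so there is no conflict.
- *That the analyses are compromised.* The exposure-QTcF analysis uses plasma concentration, so a different dose mainly moves a patient along the exposure axis. Efficacy is descriptive with no formal testing, and very few patients are involved.
- *That the restart dose would go unrecorded.* Section 10 already requires all dosing information in the eCRF.

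**Conclusion.** The inconsistency is real and narrow. For a grade 3 or 4 QTcF event with an electrolyte abnormality, the two sections give different resumption doses, 40 mg apart for a patient on 280 mg, and precedence is not stated. In practice it concerns mainly grade 3, since withdrawal criterion 7 separately lists grade 4 adverse events.

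The conclusion assumes that at least some events meeting the millisecond triggers are grade 3 or higher. That is plausible from Table 6 but cannot be confirmed from the documents. The number affected is probably a handful at most and may be zero.

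This is a low-severity internal inconsistency, not a choice of design. It merits correction because it concerns a safety instruction for the drug's most common related reaction. Nothing here bears on which dose is right.

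**What to change.** Reconcile Sections 8.5.2 and 8.5.3 by stating which one governs the resumption dose after a QTcF event. This could be an exception in the grade 3 or 4 sentence of Section 8.5.2 that refers to Section 8.5.3, or a statement in Section 8.5.3 that the Section 8.5.2 rule also applies on re-challenge. The same text should cover a repeat event after same-dose re-challenge and confirm whether the 21-day hold limit applies. The sponsor's medical team decides the content.

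The cost is a sentence or two in the next amendment, with no change to data collection, sample size or analysis.

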Study Drug Administration	For all dosing days, no food should be consumed for at least 2 hrs before and 1 hr after dosing. Patients will dose in the clinic on all PK days. Patients will track meal times on their home dosing logs.			Continuous daily administration from Cycle 1 Day 1 until one or more withdrawal criterion is met (see Section 7.4.3).						
Safety Assessments										
Physical examination	Full physical at screening, and targeted physical based on adverse events at subsequent visits. ECOG at screening.		X	X	X	X	X	X	X	X
Vital signs	BP, heart rate, respiration, and body temperature. In addition, on cycle 1 day 1, blood pressure and heart rate will be measured prior to dose administration and		X	X	X	X	X	X	X	X

Study Procedures	Notes	Pre-Screening	Screening	Cycle 1 (28 days)				Cycles 2+ (28 days)	End of Treatment	Follow-Up (EOT+28 days)
			Day -28	Day 1	Day 8	Day 15	Day 22	Day 1		
	hourly (± 15 minutes) for the first 6 hours following the first dose.									
Physical measurements	Height and weight at screening. Weight only is taken prior to each cycle and at EOT visit.		X	X				X	X	X
Hematology	Hemoglobin, RBC count, platelet count, WBC count with differential and absolute neutrophil count.		X	X		X		X	X	(X)
Coagulation	PT, aPTT, INR, and fibrinogen.		X	X				X	X	(X)
Serum chemistry	Serum chemistry parameters are listed in Section 12.1.2 . In addition, direct bilirubin is evaluated at screening if total bilirubin is > 1.5 ULN. Iron studies (serum iron, ferritin, and total iron binding capacity).		X	X		X		X	X	(X)
Fasting lipid panel	Total cholesterol, HDL cholesterol, LDL cholesterol, and triglycerides.		X					X (Every 3 cycles: C3, C6, etc.)	X	
TSH			X					X (Every 3 cycles: C3, C6, etc.)	X	
Urinalysis	Urinalysis parameters are listed in Section 12.1.2 . If dipstick result is abnormal, microscopy will be used to evaluate sediment.		X	X				X	X	
12-lead ECG	12-lead ECGs will be performed in triplicate (approximately 2 minutes between recordings) pre-dose at all visits indicated. On cycle 1 day 15, ECGs in triplicate will be completed pre-dose and 6 hours post-		X	X	X	X (Pre-dose and 6 hours post-dose)	X	X	X	X

Study Procedures	Notes	Pre-Screening	Screening	Cycle 1 (28 days)				Cycles 2+ (28 days)	End of Treatment	Follow-Up (EOT+28 days)
			Day -28	Day 1	Day 8	Day 15	Day 22	Day 1		
	dose (+/- 15 min). Refer to Section 8.5.3 for management of QTcF prolongation.									
Pharmacokinetics and Pharmacodynamics										

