7.2. Patient Inclusion Criteria

Each potential patient must satisfy all of the following criteria to be enrolled in the study:

Part 1 Only

1. Must have received at least 2 prior therapies approved for CRPC; including a prior AR inhibitor (e.g., enzalutamide or apalutamide).

Part 2 Only

1. Must have received enzalutamide or apalutamide.
 - (Note: additional therapies approved for CRPC prior to enzalutamide or apalutamide are allowed).

Parts 1 and 2

1. Histologically confirmed adenocarcinoma of the prostate with metastatic disease.
2. Male ≥ 18 years of age.
3. Eastern Cooperative Oncology Group performance status of 0 or 1.
4. Prior orchiectomy or serum testosterone levels < 50 ng/dL determined within 4 weeks prior to start of study drug.
5. Adequate baseline organ function as defined below:

Hematology	
Hemoglobin	≥9 g/dL (or ≥90 g/L) with or without transfusion
Platelet count	≥75 x 10 ⁹ /L with or without transfusion
Neutrophil count	absolute neutrophil count ≥1.0 x 10 ⁹ /L
Chemistry	
Total bilirubin	≤1.5 times laboratory upper limit of normal (ULN); patients with Gilbert's syndrome can enroll if conjugated bilirubin is within normal limits
Alanine aminotransferase and aspartate aminotransferase	≤2.5 times the ULN
Serum creatinine	<1.5 mg/dL, or a calculated or measured creatinine clearance >50 mL/min/1.73 m ²
Cardiac	
Electrocardiogram QTcF	<450 ms (average of 3 readings approximately 2 minutes apart)

6. Ongoing androgen depletion therapy with a gonadotropin-releasing hormone (GnRH) analog or inhibitor, or orchiectomy (i.e., surgical or medical castration). Note: patients who have not undergone orchiectomy must continue GnRH analog therapy for the duration of this protocol.
7. For patients previously treated with first generation anti-androgens (i.e., flutamide, nilutamide, or bicalutamide), discontinuation of flutamide or nilutamide therapy must occur >4 weeks (>6 weeks for bicalutamide) prior to start of study drug with no evidence of an anti-androgen withdrawal response (i.e., no decline in serum PSA).

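### Section 8.5.3 allows restart after a QTcF hold on an absolute QTcF below 450 ms alone, so a patient with a baseline below 390 ms can restart while still more than 60 ms above baseline

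*Combined protocol and SAP*

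**What the plan says.** The hold rule in Section 8.5.3 has a relative limb and an absolute limb: "If > 60 ms change from baseline occurs OR QTcF > 500 ms, TRC253 should be held and electrolytes evaluated and repleted (if required").

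The same section gives two ways back onto drug:

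- **Same dose.** This route is for patients who had an electrolyte abnormality when the QTcF prolongation was detected. They may be re-challenged if, "after repleting electrolytes, the QTcF recovers to < 450 ms, and a favorable benefit-risk exists per the Investigator", and they re-consent.
- **240 mg.** This route is for patients without an electrolyte abnormality who are responding and have a favorable benefit-risk. Such a patient "may resume treatment at this lower dose after recovery of the QTcF to < 450 ms". The exception to permanent discontinuation that opens this route also asks for re-consent.

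Section 7.2 sets the eligible baseline QTcF at "<450 ms (average of 3 readings approximately 2 minutes apart"), with no lower limit.

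The 60 ms change appears elsewhere as a limit too. Table 6 (Section 5.2) counts an "increase in QTcF of > 60 ms from baseline" as a DLT. Section 7.4.3 uses it in withdrawal criterion 8, and Section 8.5.3 uses it for central-reader alerts to sites.

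**The concern.** The drug is stopped on a relative or an absolute criterion but restarted on an absolute one only. For a patient with a low baseline who was held on the relative limb, QTcF below 450 ms does not show that the reason for the hold has gone. Read literally, the text lets an investigator resume daily dosing, at the full dose on the electrolyte route, while QTcF is still beyond the plan's own hold, DLT and alert limit.

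QTcF prolongation is this drug's main toxicity. The safety results in Section 2.4 report it in 22 of 34 patients (65%), two of them at grade 3, and the single DLT was a QTcF event.

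The plan does not schedule a prompt recheck after restart. The extra monitoring in Section 8.5.3, "with a minimum of weekly QTcF assessments for at least two weeks and one QTcF assessment after four weeks", applies to patients who discontinue. For those who restart, Table 8 governs Part 2: "12-lead ECGs will be performed in triplicate (approximately 2 minutes between recordings) pre-dose at all visits indicated". Those visits are weekly in Cycle 1 and then fall only on Day 1 of each 28-day cycle. A patient restarted early in Cycle 2 or later could go up to about 28 days before the next scheduled ECG.

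The dose rule also becomes unclear. Section 8.5.3 reduces to 200 mg for a subsequent change above 60 ms at 240 mg. If the patient restarted while still above 60 ms, the next ECG could be read as a new event or as the unresolved one.

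**Working it through.** **Inputs**

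- Hold: QTcF − B > 60 ms, or QTcF > 500 ms (Section 8.5.3), where B is the patient's baseline.
- Restart, both routes: QTcF < 450 ms (Section 8.5.3).
- Eligible baseline: B < 450 ms, no lower bound (Section 7.2).
- Section 14.4 defines the safety baseline as the last value before study drug starts.

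The plan states no figure of its own to reproduce here. The check compares the two thresholds.

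**When both conditions hold.** On the relative limb both are met when B + 60 < QTcF < 450. Such values exist only if B + 60 < 450, that is B < 390 ms. The width of the overlap is 450 − (B + 60) = 390 − B. The change from baseline allowed at restart is anything under 450 − B. On the absolute limb QTcF cannot be both above 500 and below 450 ms, so there is no overlap.

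| Baseline B (ms) | Hold if QTcF above B + 60 | Overlap with restart (< 450) | Width 390 − B | Change allowed at restart, 450 − B | Restart limit if change ≤ 60 ms were added |
|---|---|---|---|---|---|
| 360 | 420 | 420–450 | 30 | just under 90 | ≤ 420 |
| 370 | 430 | 430–450 | 20 | just under 80 | ≤ 430 |
| 380 | 440 | 440–450 | 10 | just under 70 | ≤ 440 |
| 385 | 445 | 445–450 | 5 | just under 65 | ≤ 445 |
| 390 | 450 | none | 0 | just under 60 | < 450 (unchanged) |

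Enumeration over whole milliseconds agrees. The largest whole-number baseline with an overlap is 388 ms (449 − 388 = 61). There is none at 389 ms or above.

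**Example.** With B = 380 ms, a QTcF of 448 ms is a change of +68 ms and calls for a hold. If it falls to 442 ms, the change is +62 ms. The hold criterion is still met, and the restart condition (442 < 450) is met as well.

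**How often.** The documents available for this review give neither a baseline QTcF distribution nor a count of holds for a change above 60 ms. The nearest figure is 2 discontinuations for QTcF prolongation among 34 patients: 2/34 = 5.9%, exact 95% CI 0.7% to 19.7%. This counts discontinuations, not holds or restarts, so it gives only a rough sense of scale.

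**The case against.** The strongest answer is that Section 8.5.3 should be read as a whole. Its opening hold rule is not confined to the first abnormal ECG, so a restart ECG at +62 ms would itself call for a hold. That is probably what the authors intend. But the section does not say which rule governs, and the restart sentences give their own numeric condition.

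Other points on that side:

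- **Recovery implies improvement.** This is fair: a patient held at 442 ms and still at 442 ms has arguably not recovered. A fall from 448 to 442 ms does satisfy the word and leaves the change above 60 ms.
- **Persistent prolongation after repletion could count as prolongation without an electrolyte abnormality.** A non-responder would then be permanently discontinued. However, the re-challenge sentence looks to electrolyte status at the time the prolongation was detected, so the text does not lead there.
- **The general rule in Section 8.5.2 asks for recovery to grade 1 or baseline.** Section 8.5.3 is the specific QTcF rule and does not refer to it.
- **There are other safeguards.** A third party over-reads all ECGs and alerts sites to changes above 60 ms, a physician reviews readings, and unscheduled ECGs are possible. These reduce the risk, but none is a restart limit. An alert on the very ECG that permits restart would give the site opposite signals.
- **Few patients are affected, and their absolute QTcF at restart is below the enrolment cap.** This stands, and it limits how serious the point is.

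**Conclusion.** The point holds. For every baseline below 390 ms, the hold and restart rules in Section 8.5.3 can be met by the same QTcF value. The overlap is 390 − B ms wide, and the residual change allowed at restart is just under 450 − B ms: 70, 80 and 90 ms at baselines of 380, 370 and 360 ms. Baselines of 390 ms or more, and holds triggered by QTcF above 500 ms, are unaffected.

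The arithmetic needs no assumption beyond the stated thresholds. The practical consequence assumes an investigator who applies the restart sentences as written. The number affected is unknown and likely small, because a low baseline, a hold on the relative limb, response or a corrected electrolyte abnormality, favorable benefit-risk and re-consent must all coincide. It should still be fixed: the rule contradicts itself on the drug's main toxicity, and the correction is simple.

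**What to change.** In both restart sentences of Section 8.5.3, require QTcF below 450 ms **and** a change from baseline of no more than 60 ms, on an ECG taken after the one that triggered the hold. The overlap then disappears at every baseline, and the limit for baselines of 390 ms or more does not move. The medical monitor or the safety committees may prefer a stricter limit on the change; 60 ms is the least that makes the section consistent.

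The cost is one added clause in each of two sentences. No new procedure is needed, because the ECG that documents QTcF below 450 ms also gives the change from baseline. The downside is that a few low-baseline patients would be held longer. Since Section 8.5.2 says "Dose interruptions are allowed for a maximum of 21 days", some of them, including responders, could reach that limit and be discontinued.
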